Consolidation or maintenance therapy with additional purine analog in preventing relapse or disease progression following purine analog treatment has not been formally evaluated, but the clinical impression is that repeated courses of purine analog have increasing cumulative toxicity with decreasing benefit, and should not be added unless patients require retreatment due to cytopenias. Moreover, cytopenias due to disease requiring retreatment must be differentiated from cytopenias due to toxicity, and it is very rare for retreatment within 6 months after prior purine analog therapy to be advisable. Most patients have relapsed disease by 16 years [Else, 2009]. There is no plateau on the disease-free survival curves to suggest that purine analogs can cure HCL [Goodman, 2003; Else, 2009]. At a median of 16 years after treatment, the Scripps population of 358 subjects contained 19 who were still being followed in continuous complete remission, nine of whom were still without evidence of minimal residual disease (MRD) [Sigal, 2010]. Thus, it is not clear if purine analogs have curative potential, but clearly they fail in most patients who live long enough. Multiple immune defects present in HCL appear to have a role in the development of second cancers. Skin cancers were found to be the most numerous before the availability of nucleoside

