5.4.1.1.8 HCL

1. Histologically confirmed diagnosis of HCL according to morphological and immunophenotypic criteria of WHO classification [[WHO, 2008](#)] of lymphoid neoplasms.
2. Must have either:
 - **Refractory disease** defined as no response or disease progression in ≤ 1 year following first-line treatment with a purine analog (i.e., pentostatin, cladribine or fludarabine)
OR

- **Relapsed** disease defined as having relapsed following treatment with at least two prior treatments
3. Must have the presence of leukemic cells in the peripheral blood or BM aspirate or BM biopsy AND one or more of the following:
 - Bulky/symptomatic splenomegaly
 - Hemoglobin <10 g/dL
 - Platelets <100 × 10⁹/L
 - Absolute neutrophil count (ANC) <1 × 10⁹/L
 4. For subjects with an opportunistic infection: the infection must be adequately managed and the subject must be clinically stable. The investigator may discuss this issue with the Medical Lead.

5.4.1.1.9 MM

1. Histologically confirmed secretory MM.
2. Has received at least 2 prior lines of therapy, such as prior treatment with a proteasome inhibitor and IMiD, and is now refractory or has demonstrated intolerance (despite standard measures of supportive care and dose reduction) to the most recent therapy received
3. Must have measurable disease of MM as defined by at least **ONE** of the following:
 - Serum M-protein ≥1 g/dL (≥10 g/L)
 - Urine M-protein ≥200 mg/24 hr
 - Serum free light chain (FLC) assay: involved FLC level ≥5 mg/dL (≥50 mg/L) and an abnormal serum FLC ratio (<0.26 or >1.65), or
 - Biopsy proven plasmacytoma (measured within 28 days of Screening)
4. **For subjects with an opportunistic infection:** the infection must be adequately managed and the subject must be clinically stable. The investigator may discuss this issue with the Medical Lead.

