5.4.2 Exclusion Criteria

ANY subject who meets any of the following criteria is excluded from enrollment in this study:

1. Prior treatment with:
 - BRAF and/or MEK inhibitor(s)
 - Chemotherapy, immunotherapy, biologic therapy or chemoradiation with delayed toxicity within 21 days (or within 42 days if prior therapy contains nitrosourea or mitomycin C) prior to enrollment
 - Chemotherapy or biologic therapy without evidence of delayed toxicity within 14 days prior to enrollment
 - Investigational product(s) (IP) within 30 days or 5 half-lives, whichever is longer, prior to enrollment
 - **Subjects enrolled in France:** Subject has participated in any study using an IP(s) within 30 days prior to enrollment in this study.
2. History of malignancy with confirmed activating RAS mutation at any time.
NOTE: Prospective RAS testing is not required. However, if the results of previous RAS testing are known, then those results must be used in assessing eligibility.

3. Prior radiotherapy less than 14 days prior to enrollment, except for WHO Grade 1-4 glioma and ATC. Treatment-related AEs must have resolved prior to enrollment.
For WHO Grades 1, 2, 3, or 4 Glioma ONLY: Radiotherapy is not permitted within 3 months prior to enrollment (extended period of time of > 3 months needed to prevent subjects with pseudo-progression from radiotherapy from being enrolled in the study). Subjects may be ≥ 2 weeks from radiotherapy if a new lesion relative to the pre-radiation MRI develops outside the primary radiation field. Treatment-related AEs must have resolved prior to enrollment.
For ATC Only: Radiotherapy is not permitted within 7 days prior to enrollment. Treatment-related AE(s) must have resolved prior to enrollment.
4. Prior major surgery less than 14 days prior to enrollment. Any surgery-related AE(s) must have resolved prior to enrollment.
5. Prior solid organ transplantation or allogenic stem cell transplantation (alloSCT)
NOTE: Previous autologous BM transplant (autoSCT) or autologous peripheral blood stem cell transplant (PBSCT) is permitted.
6. History of another malignancy
NOTE: Subjects with another malignancy are eligible if:
 - a. disease-free for 3 years, or
 - b. have a history of completely resected non-melanoma skin cancer, and/or
 - c. have an indolent second malignancy(ies).
Consult a Medical Lead if unsure whether second malignancies meet requirements specified above.
7. Presence of:

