10.1 Permitted Medications and Non-Drug Therapies

Subjects should receive full supportive care during the study, including transfusions of blood and blood products, and treatment with antibiotics, anti-emetics, anti-diarrheals, and analgesics, and other care as deemed appropriate, and in accordance with their institutional guidelines. Use of anticoagulants such as warfarin is permitted however, caution should be exercised and additional INR monitoring is recommended when dabrafenib is used concomitantly with warfarin.

Radiation: While subjects are on study treatment, palliative radiation therapy is permitted for non-target lesions that are either new or present at baseline. Radiation skin injury has been reported with concurrent use of dabrafenib and radiation. It is recommended that dabrafenib be held for 7 days before and 2 days after radiotherapy in subjects receiving dabrafenib monotherapy or in combination with trametinib. These recommendations can be modified based on the physician's assessment of the risk of radiation skin injury.

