21.12 Appendix 12: Response Criteria for HCL

Response status for hairy cell leukemia (HCL) will be assessed according to the following criteria adapted from the NCCN guideline - Consensus Resolution, and previous HCL studies.

Complete response (CR) with or without Minimal Residual Disease (\pm MRD):

- No evidence of leukemic cells by routine and H/E stains of the peripheral blood and bone marrow (BM).
- MRD: CR with HCL evident in blood by flow cytometry (FACS) or in BM biopsy by immunohistochemistry (IHC)
- No hepatomegaly, splenomegaly, or abnormal ($< 2\text{cm}$ minimum length) lymphadenopathy by appropriate radiographic techniques.
- **NOTE:** Enlarged liver or spleen associated with a negative nuclear medicine study will not prevent consideration of CR for those subjects meeting all other criteria.
- Normal complete blood count (CBC) as exhibited by: absolute neutrophil count (ANC) $\geq 1.5 \times 10^9/\text{L}$, platelets $\geq 100 \times 10^9/\text{L}$, and hemoglobin $\geq 11 \text{ g/dL}$ without transfusions or growth factors for at least 4 weeks.

After this 4-week period, BM biopsy and computed tomography (CT) scan must be performed to confirm CR. The BM biopsy and aspirate need not be performed at the beginning of this 4-week interval.

Complete response (CR): defined as the complete disappearance of all evidence of disease and requires all of the following:

- Normal CBC as exhibited by: ANC $\geq 1.5 \times 10^9/\text{L}$, platelets $\geq 100 \times 10^9/\text{L}$ and hemoglobin $\geq 11 \text{ g/dL}$
- Absence of hairy cells (by morphological examination) in the peripheral blood and in the BM
- Regression to normal of disease-related organomegaly

Confirmation of CR: At the confirmatory ≥ 6 month visit, a BM biopsy, hematology, immunoglobulins and flow cytometry will be reassessed.

Duration of CR: The duration of complete remission is calculated from the time of achievement of all criteria of CR to the time of relapse from CR.

Partial response (PR): requires all of the following for a period of at least 4 weeks:

- Normal peripheral blood counts (as in CR)
 - $ANC \geq 1.5 \times 10^9/L$ or 50% improvement over baseline without growth factors for at least 4 weeks, **AND**
 - Platelets $\geq 100 \times 10^9/L$ or 50% improvement over baseline, **AND**
 - Hemoglobin ≥ 11 g/dL or 50% improvement over baseline without transfusions or growth factors for at least 4 weeks.

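### HCL response: the PR platelet line in Appendix 12 does not exclude transfused or growth-factor-supported values, and baseline can predate the end of prior therapy; no planned analysis shows the effect of either

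*Protocol*

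**What the plan says.** **Response criteria (protocol Appendix 12).** The PR count block is headed "Normal peripheral blood counts (as in CR"). Beneath it, the neutrophil line excludes growth factors for four weeks and the hemoglobin line excludes transfusions and growth factors for four weeks. The platelet line accepts 100 × 10⁹/L or a 50% improvement, with no condition on support. PR also needs circulating hairy cells at or below 5% of lymphocytes and at least a 50% reduction in both marrow infiltration and palpable organomegaly, all for at least four weeks. CR is defined twice. CR with or without MRD requires four weeks of counts free of transfusion and growth factors; the second definition gives the same thresholds without that condition.

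**Supportive care (protocol 10.1).** "Subjects should receive full supportive care during the study, including transfusions of blood and blood products".

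**Entry.** Section 5.4.2 excludes "Chemotherapy, immunotherapy, biologic therapy or chemoradiation with delayed toxicity within 21 days" (42 days for nitrosourea or mitomycin C) and "Chemotherapy or biologic therapy without evidence of delayed toxicity within 14 days prior to enrollment". Section 5.4.1.1.8 accepts refractory disease, meaning no response or progression within a year of a first-line purine analog, or disease "having relapsed following treatment with at least two prior treatments". It sets no interval since the last course and no minimum time before non-response may be judged. Table 4, footnote 34, allows the baseline marrow up to 28 days before enrollment.

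**Background (protocol 1.5.8).** On timing, the protocol says that "it is very rare for retreatment within 6 months after prior purine analog therapy to be advisable". It also warns that low counts from the leukemia have to be told apart from low counts caused by treatment.

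**Analysis.** SAP 2.4.1 counts CR without MRD, CR with MRD and PR as response, derived from investigator assessments and confirmed at least 28 days later (Table 2-4). SAP 2.6.2 notes that HCL has no independent review, and SAP 2.4.4 does not include HCL. Blood products are summarized (SAP 2.1.1) but not linked to response.

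**The concern.** HCL is judged in a single arm against a fixed 10% historical rate (protocol Table 29). Any response not caused by the combination therefore counts as activity, and there is no concurrent arm to show it. Two routes are open.

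The first is platelet support. Applied as written, Appendix 12 lets a transfused platelet value fill the one count component that lacks an exclusion. The appendix itself expects transfusion-dependent subjects, because it sets a separate hemoglobin rule for them.

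The second is timing. If the baseline marrow was taken before the previous course had ended, any further effect of that course is measured as change on study. Such an effect could move marrow, hairy cells and counts together, so the multi-component PR definition would not screen it out.

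At stake is the credibility of the HCL ORR in the final report, and less plausibly the declaration of activity itself.

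**Working it through.** **1. Supported counts, line by line (Appendix 12).**

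| Component | Transfusion excluded | Growth factors excluded |
|---|---|---|
| CR with or without MRD, all counts | yes | yes |
| Second CR definition, all counts | not stated | not stated |
| PR hemoglobin | yes | yes |
| PR neutrophils | not stated | yes |
| PR platelets | not stated | not stated |

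The PR heading does not settle the platelet line, because the lines beneath it already depart from CR by allowing a 50% improvement. For example, a transfused rise from 20 to 30 × 10⁹/L gives 30/20 = 1.5 and meets that line. All other PR items must still hold.

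**2. Timing of baseline.** Marrow is allowed up to day −28 from enrollment, and chemotherapy may end at about day −14 or −21. The marrow sample can therefore precede the last dose by up to 28 − 14 = 14 days, or 28 − 21 = 7 days.

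**3. The plan's own operating characteristics.** The clustered model of Appendix 6 was rebuilt (α = 2, μ variance 3, τ² ~ IG(3, 0.5)) and compared with Appendix 8.
- HCL posterior in Examples 1 to 6: stated 1, 0.21, 0.97, 0.97, 1, 0.30; computed 1.00, 0.23, 0.97, 0.97, 1.00, 0.31.
- Over all 54 posteriors the largest difference is 0.026, and every decision agrees.
- Simulated HCL type I error (Case 1, Null, 1000 trials): 0.045 (SE 0.007), against at most 0.04 stated.
- Simulated HCL power (Alternative): 0.983, against 93% to 98% stated for the larger cohorts.

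**4. Sensitivity to false responses (assumed).** Let m be the share of true non-responders counted as responders. The apparent rate at the null is 0.10 + 0.90m. With the other cohorts at their null rates:

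| m | Apparent rate | P(HCL declared active) |
|---|---|---|
| 0 | 0.10 | 0.045 |
| 5% | 0.145 | 0.104 |
| 10% | 0.19 | 0.225 |
| 20% | 0.28 | 0.479 |

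**5. No-borrowing check, n = 20 (HCL projection in Cases 3 and 4 of Table 32).** The prior on the log-odds shift is normal with variance 3.25, that is 3 plus the mean of IG(3, 0.5), 0.5/(3 − 1) = 0.25. The posterior P(π > 0.10) is 0.874 with 4 responders and 0.958 with 5, so 5 are needed to pass 0.92. P(X ≥ 5 | 20, 0.10) = 0.043. With k certain false responders, P(Bin(20 − k, 0.10) ≥ 5 − k) = 0.115, 0.266 and 0.518 for k = 1, 2, 3.

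**6. Effect on the reported ORR.** One response is 1/20 = 5 points at n = 20. The Amendment 11 rationale lists 36 HCL subjects on treatment and 7 in follow-up, so the combined cohort has at least 43 and one response there is at most 1/43 = 2.3 points.

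**The case against.** The strongest reply is that HCL response does not rest on blood counts. PR needs marrow, hairy-cell and organ improvement held for four weeks, CR needs hairy cells gone from blood and marrow, and the SAP adds confirmation at 28 days and does not count minor response. Transfusion does not clear marrow. This stands. A reader might infer that transfusion alone could produce a PR; Appendix 12 does not allow that.

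Entry is also partly guarded. Exclusion 7 bars unresolved Grade 2 or higher toxicity from earlier cancer therapy (Grade 2 anemia exempt), and Table 3, note 3, waives count minimums only when cytopenias are due to the disease. Both depend on the investigator's attribution of the cytopenia, so the protection is partial.

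A reader might also take the six-month remark in 1.5.8 as an entry standard that the protocol then breaks. It is background on repeating purine analogs, not an eligibility rule for another drug class. Nor does any passage say how often marrow clears late after such a course. The carry-over route is therefore a possibility that the rules leave open, not a documented effect.

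Finally, the SAP reports HCL complete-response duration, the proportion lasting at least 180 days and time to response (2.6.1), and it summarizes and lists prior therapy and blood products. These would help a reader to spot transient responses. None relates a response to platelet support or to time since a purine analog.

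**Conclusion.** The point holds in limited form. Appendix 12 is inconsistent on supported platelets and between its two CR definitions, and a supported value can complete a PR that otherwise qualifies. The entry and baseline windows allow a baseline marrow that predates the end of the previous therapy. With no independent HCL review and no linking analysis, the report could not show whether either route mattered.

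The size is unknown, because the documents do not give the number of subjects affected. The 12%, 27% and 52% are conditional on one, two or three assumed false responders, with 20 subjects, no borrowing and no interim looks. A reader might take them as the trial's false-positive rate; they are not. The m values are likewise assumptions.

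The declaration of activity may well be safe: the clinically meaningful rate is 50%, far above the 5-of-20 margin, and the Amendment 11 rationale reports durable HCL responses. The exposure is mainly to the ORR estimate. The change should be made, because this is the primary endpoint and the data are already collected.

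**What to change.** 1. **Appendix 12.** Reconcile the PR platelet line and the two CR definitions with the four-week condition, no transfusions and no growth factors, that CR with or without MRD already carries.
2. **SAP 2.4.4, HCL sensitivity analysis.** Repeat confirmed ORR and the model result without counting a PR or CR when a platelet transfusion or platelet growth factor is recorded in the 28 days before that response assessment. Show the number affected, and state which category such an assessment takes in the Table 2-4 algorithm.
3. **HCL tabulation.** Give the time from last purine analog to first study dose and to baseline marrow, and show ORR by that interval. Do not score all recent purine-analog subjects as non-responders, since that would turn genuine responders into failures.

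No washout length is proposed. How the entry windows relate to Section 1.5.8 is for the sponsor to reconcile.

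The cost is a wording correction, one derivation and one table, from prior-therapy, blood-product and concomitant-medication dates already collected. Enrollment closed in June 2018, so no subject's entry changes. The HCL ORR may be lower in the sensitivity analysis. If no subject is affected, the tables close the question.

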1.5.9 Cohort 9: Multiple Myeloma (MM)

Multiple myeloma (MM) is a systemic malignancy of plasma cells in the BM that secretes all or part of a monoclonal antibody. It is the second most common hematologic malignancy, accounting for 10% of all hematologic cancers and 2% of annual cancer-related deaths [Anderson, 2011]. The incidence of multiple myeloma in the US in 2008 was 5.579 per 100,000 [Ferlay, 2011] According to the ACS, it was expected that almost 21,700 new cases of MM and 10,700 MM related deaths would occur during 2012 [ACS, 2012].

Chapman et al and Walker et al genotyped MM patients and detected the BRAF V600E mutation in 2.4% and 4%, respectively [Chapman, 2011b; Walker, 2012]. The finding of BRAF mutations in patients with MM has important clinical implications because such patients may benefit from treatment with a BRAFi. These results also support the observation that inhibitors acting downstream of BRAF (i.e., MEK) may have activity in MM [Kim, 2010].

Multiple myeloma (MM) is further classified on the basis of the patient's characteristics. Patients who are younger than 65 years of age and without other severe co-morbidities are considered eligible for allogeneic stem cell transplantation (alloSCT). Patients older than 65 years or with serious co-morbidities are usually not considered SCT candidates and a gentler

approach is needed. Although MM is not curable, it is treatable. The median survival with chemotherapy is 24 to 30 months with a 10-year survival rate of 3%. With newer therapies of immunomodulatory drugs (IMiD: thalidomide, lenalidomide), proteasome inhibitor (bortezomib) and stem cell transplantation, the median OS has been prolonged 7 to 8 years [Kumar, 2008; Anderson, 2011].

In the bortezomib registration study of over 600 subjects, the response rate to bortezomib and dexamethasone for subjects with MM relapsing after at least one systemic therapy not containing bortezomib was 38% [Richardson, 2005]. The PFS for the bortezomib arm in this study was 6.2 months (median follow-up of 8.3 months). A subset analysis showed that the ORR and survival was higher for the less heavily pre-treated subjects. Amongst the IMiDs, both thalidomide and lenalidomide have been extensively investigated in the induction/consolidation/maintenance settings and both agents have been approved by the US FDA.

Despite these agents and along with other agents such as carfilzomib and pomalidomide, MM continues to remain incurable. In particular, patients resistant to novel agents represent a challenging group. Kumar et al. conducted an analysis in subjects who relapsed or were refractory to one of the IMiDs as well as bortezomib that determined the median event-free survival to be 5 months and the median OS was 8 months [Kumar, 2010]. Therefore, these patients require novel strategies.

2 RATIONALE

2.1 Rationale for the Combination of Dabrafenib and Trametinib

Pre-clinical studies have demonstrated that the combination of dabrafenib and trametinib is synergistic and/or enhances cell growth inhibition in majority of the BRAF V600E mutant melanoma, colon, thyroid, and lung cancer cells. The combination delayed dabrafenib resistance and reduced hyperproliferation skin adverse effect in pre-clinical models. The scientific rationale suggesting MEK-mediated re-activation of the MAPK pathway as a prominent mechanism of resistance to BRAFi single-agent therapy supports the combination study of trametinib with BRAFi in cancer [Alcala, 2012; Greger, 2012]. Because BRAF V600E mutated tumors have been shown to develop resistance to BRAF inhibitors, the combination of a BRAFi and MEKi provides a rational approach for dual vertical inhibition within the MAPK pathway to address such drug resistance [Johannessen, 2010]. Both have demonstrated substantial clinical activity with ORR between 28 to 53% and PFS ranging between 4.8 to 5.1 months. Further, the combination of both dabrafenib and trametinib indicated increased efficacy over both monotherapies with ORR of 63% and an increase of PFS to approximately 10 to 11 months for the 150 mg BID dabrafenib and 2 mg once daily trametinib dose cohort [Flaherty, 2012; Hauschild, 2012; Weber, 2012]. Furthermore, the combination of dabrafenib and trametinib has demonstrated overall survival of a median of more than 25 months in advanced melanoma. This robust survival data for the combination is further supported by other efficacy measures such as progression free survival of >11 months, overall response rates of about 64-69% (13-16% of patients achieving a complete response) with duration of response of 12.9-13.8 months and a disease control rate of 94% across two randomized Phase-III studies. (Long GV, 2015; Robert C, 2015).

Substantial safety and efficacy data across these clinical development programs in metastatic melanoma demonstrated the scientific validity of dual inhibition targeting the MAPK

pathway through dabrafenib and trametinib in human cancer. The combination therapy of dabrafenib + trametinib may offer greater benefit to BRAF V600E mutated cancers than either agent alone.

